The proposed study uses a novel medication regimen, i.e., concomitant cinacalcet use, to make teriparatide effective in these patients. Teriparatide treatment alone in CKD-5 D patients with low turnover bone lossosteoporosis and elevated PTH does not result in an increase in bone formation markers.²⁵

This study will provide innovative targeting of bisphosphonates to the normal to high turnover CKD-5D patient population. There are a few uncontrolled studies of bisphosphonate treatment in CKD-5D but these do not separate high from low bone turnover.^{19, 21-23} This study will produce new data indicating whether these treatments will retard the relentless progression of CAVC in CKD-5D patients associated with the cardiovascular events responsible for mortality rates exceeding many cancers.

Moreover, new insights will be gained into the specific links between bone and CAVC outcomes and FGF23, indicators of Wnt pathway and markers of bone formation and resorption.

Upon completion of the study, we will, for the first time, make it possible to effectively manage CKD-associated bone lossosteoporosis in both black and white patients.

Objectives: List your research objectives. You may reference grant application/sponsor's relevant protocol pages and attach as an appendix in the E-IRB "Additional Information" section, however, a summary paragraph must be provided in the text box below.

Specific Aim #1: Evaluate a novel individualized treatment regimen for low bone densityosteoporosis in CKD-5D patients. For this purpose, CKD-5D patients with established low bone densityosteoporosis will be enrolled into one of two treatment arms based on bone turnover status; low versus normal-high. Each arm will be randomized into treatment or control groups. In the low turnover arm, teriparatide combined with cinacalcet will be given to stimulate bone formation, and in the normal-high turnover arm, alendronate will be administered to reduce bone resorption. We will monitor safety and response by patient assessments and blood draws at regular visits and telephone calls. The primary endpoint for Specific Aim #1, bone mineral density (BMD), will be measured by quantitative computed tomography (QCT) at baseline, 6 months and after one year and two years of treatment.

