Research Repositories: If the purpose of this submission is to establish a Research Repository (bank, registry) indicate whether the material you plan to collect would or would not be available from a commercial supplier, clinical lab, or established IRB approved research repository. Provide scientific justification for establishment of an additional repository collecting duplicate material. Describe the repository design and operating procedures. For relevant information to include, see the UK Research Biospecimen Bank Guidance [\[PDF\]](#) or the UK Research Registry Guidance [\[PDF\]](#)

Patient recruitment will be done for the first 42 months of the study after administrative startup (Figure 2). Biochemical measurements, MDCT, QCT and DXA scans, and clinical assessment will be performed at baseline, 6 months, and at 12 months, 18 months and 24 months. Treatment monitoring visits with blood draws (initially bi-weekly or monthly and thereafter every 3 months) and adverse event monitoring phone calls (monthly at least) will occur during years one through five. Interim analyses and first publications will be done once 50% of patients have completed 1 year visits, approximately at the end of Year 3. Final analyses of the data and preparation of abstracts and manuscripts of the obtained results will be completed during year 5. Control patients who completed 1 year of follow up without treatment will be offered additional 2 years of enrollment with treatment according to protocol. Patients who were initially randomized to treatment groups will be offered continued treatment for an additional 1 year to complete 2 years of therapy. Previously enrolled patients will be recruited from the beginning of patient enrollment. These patients will be provided with an additional consent for the extension of the treatment arm.

Figure 2: Study Timeline

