The study coordinators will approach via phone during normal business hours all patients who completed study participation and those currently enrolled in ROD III to discuss the extended enrollment option. All previous patients will be eligible for approaching for the extension regardless of when initial participation was completed. Patients will be informed about the goals and the protocol of the study. A list of screened patients will be kept under lock and key in the study coordinators office and on a password protected computer.

Advertising: Specify if any advertising will be performed. If yes, please see ["IRB Application Instructions - Advertisements"](#) for instructions on attaching copies of the information to be used in flyers or advertisements. Advertisements must be reviewed and approved by the IRB prior to use. For additional details, see topic "Recruitment of Subjects/Advertising" on ORI's [IRB Survival Handbook](#) web page for the *PI Guide to Identification and Recruitment of Human Subjects for Research* [D7.0000] document [\[PDF\]](#). If you will be recruiting subjects via advertising at non-UK owned or operated sites, you should include a copy of written permission from that site to place the advertisement in their facilities.

Note: Print and media advertisements that will be presented to the public also require review by [UK Public Relations \(PR\)](#) to ensure compliance with UK graphic standards, and equal opportunity language. [i](#)

Print advertisements: The study may recruit subjects through flyers, brochures, posters, cards for clinic rooms, Research Spotlights, bookmarks placed on campus and in the surrounding community and region, including but not limited to the UK Medical Center, UK Clinics, Good Samaritan Hospital, student center, UHS, the 5 UK Center for Clinical and Translational Research wall mounts, Cardinal Hill, monitor screens, and area facilities and businesses.

This study may use physician referral letters to community physicians for patient recruitment.

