If previously completed or current patients are interested in the enrolling in the extended treatment option, patients will be explained all potential risks and benefits by the research coordinators. A third level of consent will be signed for the extended treatment arm. Upon agreement to participate in the study, patients will not be asked to sign the consent form immediately and will be encouraged to take time to think it over and discuss it as they wish with their primary physician and/or family member. Upon agreement, a written consent form approved by the Institutional Review Board (IRB) will be signed by each patient in the presence of a witness. To avoid the appearance of potential coercion, the PI will not seek consent to participate in the study. He will be available for answering additional questions, if needed, after the informed consent form is signed. One copy of the consent form will be given to the patient, and the original will be stored in the patient's file in the study coordinators' office under lock and key. There will not be emancipated individuals. Only English speaking individuals will be enrolled at this time.

[Back to Top](#)

Research Procedures: Describe the research procedures that will be followed. Identify all procedures that will be carried out with each group of subjects. Differentiate between procedures that involve standard/routine clinical care and those that will be performed specifically for this research project.

We will enroll and consent 990 CKD-5D patients. Patients who meet the selection criteria will be informed about the goals, procedures, and potential risks of the study treatment modalities. It will be emphasized that willingness or unwillingness to participate in any aspect of the proposed studies will not affect the patients' medical care. The protocol will be presented by the study coordinator with support of the PI as needed. Patients will be given ample time (1-2 weeks) to think about and discuss their participation with their primary nephrologist, other treating physicians, or any other persons. There will be three levels of signed consent, the first will be consent for baseline measurements and the second for treatment. The third level of consent is for current patients or those who have completed 1 year of ROD III and wish to enroll in the extended option to complete two years of medication therapy. Demographic and clinical information will be recorded at the time of signed consent.

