Patients consenting for baseline measurements will have BMD measurements of the total hip, lumbar spine and radius by DXA and total body scan. We do not use QCT for initial BMD assessment to avoid unnecessary radiation exposure to patients with normal bone mass who will be excluded from the study. Patients who are not do not have low bone densityosteoporotic by DXA T-scores/Z-

scores at any site will be excluded from further participation. Results from our prior funding period study indicate this will be 30% or 178 patients. Those patients who are identified as having low bone density/osteoporotic will have blood draws performed for determination of turnover status (PTH, PTH ratio and TRAP-5b; see Table 1) and baseline biochemical results (serum calcium and BSAP). They will also have BMD measurements of the total hip and spine by QCT, and CAVC measured by MDCT. Patients will be assigned to one of two treatment arms based on their turnover status: 1) low turnover patients and 2) normal or high turnover patients. For each treatment arm we will use adaptive randomization by group completion rates, age race and gender to assign patients to one of two groups A) treatment, and B) no study treatment (standard of care) controls.

For the extension of treatment modification, we will contact all patients who completed one year in either the treatment or control arms. Patients who previously participated in the treatment arm will be offered an additional 1 year of therapy to complete 2 years of therapy. For patients who previously participated in the control arm, they will be offered 2 years of therapy. Both therapies can be given in two consecutive years, or with a time-gap in-between.

TREATMENT PROTOCOLS:

Low Turnover Groups: Patients with low bone turnover will be randomized to receive daily teriparatide injections with cinacalcet or no study treatment, i.e. standard of care, as controls.

Normal or High Turnover Groups: Patients with normal or high bone turnover will be randomized to receive alendronate or no study treatment, i.e., standard of care, as controls. Teriparatide is not justified in these patients because it might worsen underlying high turnover abnormalities and requires avoidable daily injections.

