BSAP from blood drawn at monthly monitoring visits for the first 3 months, thereafter at quarterly monitoring visits. BSAP is expected to go down, but to avoid over-suppression, will not be allowed to go below the low normal range of the assay, as is done clinically. Our data show that mid/normal ranges of these markers in CKD-5D patients indicate low turnover^{48, 49} If this safety threshold is crossed, treatment will be stopped until values are back above the threshold at a regularly scheduled monitoring visit. Once demonstrably back within safety threshold, treatment will be reinstated at half of the initial dose (35 mgs every other week). If BSAP does not go down at least 8% over a one month period, treatment doses will be doubled to 70 mgs per week. If they still remain high, study coordinators will carefully review with the patients the mode of drug intake and possible compliance lapses.

Primary Endpoint At one year after baseline, we will assess bone mass using QCT BMD measurements of the total hip and compare 1 and 2 year changes in bone mass between the treatment and control groups. Total hip will be used as the primary endpoint site because in our prior funding period we showed that changes at the total hip in QCT BMD are more pronounced than at the spine⁶. The Secondary endpoint will be differences between the treatment and control groups in changes in coronary artery calcifications by MDCT. This will be relevant regardless of bone effects.

Other secondary endpoints tracked at baseline, 6 months, and 1 year, 18 and 24 months will include serum biochemical markers of bone activity; FGF 23, BSAP, TRAP5b, P1NP, Sclerostin, and DKK1.

Additionally we will record 1) Change in QCT BMD of the spine to compare with the hip) 2) Changes in DXA BMD of the hip and spine (to determine whether the more commonly available DXA results are equivalent to QCT and 3) Changes in aortic and heart valve calcification (to compare with the coronary artery calcifications).^{50,51} 4) Whole body composition (%fat vs %lean) as it relates to survival in CKD-5D patients.

Attachments

Attach Type	File Name
ResearchProcedures	figure 3 7.22.2019 pdf.pdf

Data Collection: List the data or attach a list of the data to be collected about or from each subject (e.g. interview script, survey tool, data collection form for existing data).

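### The primary endpoint includes a 2-year treatment-versus-control BMD comparison, but controls are offered active drug after year 1, so no reading of it is randomised treated versus untreated

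*Combined protocol and SAP*

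**What the plan says.** Research Procedures, Primary Endpoint, opens with an assessment of total hip QCT BMD one year after baseline. The same sentence then commits the trial to "compare 1 and 2 year changes in bone mass between the treatment and control groups". Specific Aim #1 (Objectives) agrees that two years is a primary-endpoint time point: BMD "will be measured by quantitative computed tomography (QCT) at baseline, 6 months and after one year and two years of treatment".

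Controls are randomised to standard of care without study treatment, but that condition is protected only for the first year. Study Design states: "Control patients who completed 1 year of follow up without treatment will be offered additional 2 years of enrollment with treatment according to protocol". The extension text in Research Procedures repeats it: "For patients who previously participated in the control arm, they will be offered 2 years of therapy".

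Year 2 is optional for patients first randomised to treatment as well; they are offered one further year. Entry is by separate agreement (Informed Consent Process): "A third level of consent will be signed for the extended treatment arm". Timing is open (Research Procedures): "Both therapies can be given in two consecutive years, or with a time-gap in-between". So is eligibility (Subject Recruitment Methods & Privacy): "All previous patients will be eligible for approaching for the extension regardless of when initial participation was completed".

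Table 2, which covers blood draws, still carries a standard-of-care control block with columns out to 2 years. Study Design lists scans to 24 months without saying whether they apply to patients who decline the extension.

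**The concern.** A treatment-versus-control comparison at two years needs a control group that is still a control group at two years. The plan offers that group the drug at month 12. It does not say how controls who switch, controls who decline, or treated patients who stop at one year enter the 2-year comparison. It also does not say whether the two years run from randomisation or from first dose.

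Because the 2-year comparison sits under the primary endpoint and is not ranked against the 1-year one, a result that is really early versus delayed start, or treated patients against self-selected decliners, could be reported as a main treatment effect. The Data and Safety Monitoring section adds to this: it allows a superiority decision without saying which time point that decision concerns.

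**Working it through.** The plan gives no effect size, uptake rate or power for the 2-year comparison, so there is no stated figure to reproduce. The check has two parts.

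**1. What the 2-year contrast could mean**

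- *From original baseline, as randomised.* Treated patients may have up to two years on drug by month 24. Controls who accept the offer at month 12 have up to one. This keeps the randomisation but estimates early versus delayed start.
- *From original baseline, untreated controls only.* Table 2's control columns to 2 years fit this reading. After month 12 that group consists of controls who declined, were not reached or had not yet started. They are self-selected, so randomisation no longer protects the contrast, and the direction of bias is unknown.
- *From start of drug.* Specific Aim #1 speaks of years of treatment, and Study Design gives controls two additional years, which suggests that the schedule restarts for them. A control who takes the full offer without a gap reaches two years on drug at month 12 + 24 = 36. Both groups are then treated, and there is no concurrent untreated randomised comparator.

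**2. Illustration of size for the first reading**

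These inputs are assumptions, not document figures:

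- each year on drug adds a gain d relative to no drug, linearly, and the gain is kept if drug stops;
- a share f of controls switches at month 12;
- a share g of treated patients continues through year 2 without a gap;
- month-24 scans are complete.

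Mean gain at month 24 is (1 + g)d in the treated group and f·d in controls. The contrast is therefore (1 + g − f)d. Uninterrupted treated versus untreated would give 2d, so the shortfall is 1 − (1 + g − f)/2.

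| f | g | contrast | shortfall against 2d |
|---|---|---|---|
| 0 | 1 | 2.00d | 0% |
| 0.25 | 1 | 1.75d | 12.5% |
| 0.50 | 1 | 1.50d | 25% |
| 0.75 | 1 | 1.25d | 37.5% |
| 1 | 1 | 1.00d | 50% |
| 0.25 | 0.5 | 1.25d | 37.5% |
| 0.50 | 0.5 | 1.00d | 50% |

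Whenever g = f the contrast is d, a 50% shortfall. It equals 2d only if no control switches and every treated patient continues.

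Later switching reduces the shortfall. If every control started at month 18 and g = 1, control gain would be 0.5d and the contrast 2d − 0.5d = 1.5d, a 25% shortfall instead of 50%. A gap among treated continuers works the other way.

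**The case against.** The best defence is that the plan already leans on year 1. The Primary Endpoint sentence starts there, and Study Design ties early reporting to it: "Interim analyses and first publications will be done once 50% of patients have completed 1 year visits". That stands. A reader might infer that the whole primary result is compromised, but the documents do not support this: controls are untreated through month 12 and the 1-year randomised comparison is unaffected.

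Second, crossover is an offer. A reader might infer that all controls switch and the contrast is halved. The text does not say so, and some controls may remain untreated to month 24. This limits any claim about size. It does not rescue the contrast, because no rule defines the remaining controls and they would not be a randomised group.

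Third, a reader might infer that only patients signing the third consent are scanned at month 24, so that every scanned control is a switcher. Study Design lists 24-month scans without that restriction. Table 2 concerns blood draws, and its column positions are lost in the supplied text. The point cannot be settled either way.

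Fourth, under the model above, analysing as randomised shrinks a benefit and is therefore conservative. That is fair for the early-versus-delayed reading, although the result would still be mislabelled. It does not cover the reading restricted to untreated controls.

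Finally, the study timeline, two attached figures and the extension consent were not supplied and may add detail. The finding therefore concerns the visible text; it does not show that no handling rule exists anywhere.

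**Conclusion.** The point holds for the 2-year element of the primary endpoint and for nothing beyond it. As written, the plan names a treatment-versus-control comparison at two years while offering the controls active drug after one, and none of the three readings of that comparison is randomised treated versus untreated.

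The size cannot be derived from the documents. Under the stated assumptions the as-randomised 24-month contrast is 12.5% to 50% smaller than 2d for f from 0.25 to 1 with full continuation. It is smaller still when treated patients stop at one year, and closer to 2d when controls start after month 12. Uptake, continuation, linearity and d are all assumed, so these figures show direction and range and are not a forecast.

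This should be fixed in the wording and analysis plan. It does not invalidate the trial.

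**What to change.** - State that 12-month change in total hip QCT BMD is the primary randomised comparison within each turnover arm. Record whether any 1-year data had been examined when this was fixed; enrolment was planned from January 2015 and interim analyses follow half of the 1-year visits. If data had been examined, report the choice as a late decision.
- Reconcile Specific Aim #1, Study Design, the extension text, Table 2 and the Primary Endpoint paragraph on what 2 years means for controls, and on whether the schedule restarts for those who switch.
- Report 24-month results as secondary. Label any between-group figure timed from original baseline as early versus delayed start, analysed as randomised with a stated missing-data assumption. Report extension data by time on drug as non-randomised.

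The cost is protocol and SAP wording plus some analysis work; the treatment offer is untouched. The trial gives up any claim to a randomised 2-year treated-versus-untreated effect. The 24-month data may also be incomplete, because the plan does not say whether patients who decline the extension are scanned then.

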Background: Provide an introduction and background information. Describe past experimental and/or clinical findings leading to the formulation of your study. For research involving investigational drugs, describe the previously conducted animal and human studies. You may reference grant application/sponsor's relevant protocol pages and attach as an appendix in the E-IRB "Additional Information" section, however, a summary paragraph must be provided in the text box below. For research that involves FDA approved drugs or devices, describe the FDA approved uses of this drug/device in relation to your protocol. Attach a copy of the approved labeling as a product package insert or from the Physician's Desk Reference in the applicable E-IRB "Study Drug" or "Study Device" section.

Background: Chronic kidney disease (CKD) is a pervasive health problem affecting more than 10% of the general population of the U.S., 31.7 million individuals.^{1, 2} Chronic kidney disease bone and mineral disorder (CKD-MBD) starts early during the loss of kidney function and is seen in virtually all CKD stage 5 patients.³ Bone loss is an integral part of renal osteodystrophy (ROD) which encompasses the bone abnormalities of CKD-MBD.^{4, 5} Our prior funding period study revealed the important findings that 30% of CKD-5D patients are osteoporotic, and that over 33% of these patients have substantial bone loss over a one year.⁶ Bone loss of the hip measured by quantitative computed tomography (QCT) showed the most severe losses. It is of note that hip fractures occur in patients with CKD-MBD at a rate that is up to 10 times higher than in the general population;⁷⁻¹² with an associated high cost and morbidity. These fractures occur 10-15 years earlier than in non-CKD patients and have an annual subsequent mortality of 64%.⁸ Additionally, CKD patients with osteopenia are at greater risk for an exponential rate of bone loss than already osteoporotic patients.

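### The primary comparison of hip BMD changes specifies no adjustment for baseline BMD or the allocation factors; a prespecified ANCOVA would be a modest gain at almost no cost

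*Combined protocol and SAP*

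**What the plan says.** The primary comparison is described in the Primary Endpoint paragraph of Research Procedures. At one year "we will assess bone mass using QCT BMD measurements of the total hip", and the investigators will "compare 1 and 2 year changes in bone mass between the treatment and control groups". The paragraph gives no test, model or covariates, and the rest of the text supplied adds none.

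Three other places bear on the choice of model.

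- **Baseline value.** Specific Aim #1 says BMD "will be measured by quantitative computed tomography (QCT) at baseline, 6 months and after one year and two years of treatment". Research Procedures places the first scan before assignment, in patients found by DXA to have low bone density: "They will also have BMD measurements of the total hip and spine by QCT".
- **Allocation.** Specific Aim #1 says "Each arm will be randomized into treatment or control groups", so there are two separate comparisons, one per turnover arm. Research Procedures says assignment uses "adaptive randomization by group completion rates, age race and gender". Baseline BMD is not an allocation factor, and no allocation ratio is given.
- **Prognosis.** The Background says "CKD patients with osteopenia are at greater risk for an exponential rate of bone loss than already osteoporotic patients". On the investigators' own account, the starting level of bone density predicts later loss.

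**The concern.** When the baseline of the primary endpoint is available and is said to predict change, a bare comparison of changes leaves usable information out. Three things are at stake.

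1. **Precision.** A change score fixes the coefficient on baseline at 1, whereas ANCOVA estimates it. If follow-up regresses on baseline with a slope below 1, the change score carries avoidable variance.
2. **Chance imbalance.** Baseline BMD is balanced only by chance, and separately within each turnover arm. The change score over-corrects for such an imbalance when the slope is below 1.
3. **Standard errors.** Allocation that balances age, race and gender makes the groups more alike on those factors than simple randomization would. An analysis that leaves them out does not credit that balance, so its standard errors are too large if the factors predict BMD change.

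**Working it through.** The text supplied has no sample size, SD of change, effect size or baseline-to-follow-up correlation for the primary endpoint, so there is no figure to reproduce. The stated QCT precision of 0.8% is measurement error only and does not give the SD of change between patients. Rho and the variance explained by age, race and gender (R²) are therefore assumed and shown over a range.

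**Step 1: variance.** Let s0 and s1 be the SDs of BMD at baseline and follow-up within a group, and rho their correlation.

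- Change score: s0² + s1² - 2·rho·s0·s1
- ANCOVA: s1²(1 - rho²)
- Difference: (s0 - rho·s1)², which cannot be negative

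These expressions assume equal allocation or common slopes. With s0 = s1 = s they become 2s²(1 - rho) and s²(1 - rho²), so the ratio of ANCOVA to change score is (1 - rho²)/[2(1 - rho)] = (1 + rho)/2.

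**Step 2: chance imbalance.** If the groups differ at baseline by d, the expected change-score difference given d is the treatment effect plus (rho - 1)·d. A fraction (1 - rho) of d remains, with opposite sign.

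| Assumed rho | Variance ratio (1+rho)/2 | Saving in N | Imbalance left in change score |
|---|---|---|---|
| 0.7 | 0.85 | 15% | 30% |
| 0.8 | 0.90 | 10% | 20% |
| 0.9 | 0.95 | 5% | 10% |
| 0.95 | 0.975 | 2.5% | 5% |

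**Step 3: what the change score already achieves.** Relative to the variance of follow-up BMD alone, at rho 0.9 the change score has 2(1 - 0.9) = 0.20 and ANCOVA has 1 - 0.81 = 0.19. At rho 0.8 the figures are 0.40 and 0.36. Most of the between-patient variance has gone before any covariate is added.

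**Step 4: age, race and gender.** If they explain a further share R² of the residual variance, multiply the ratio by (1 - R²). At an assumed R² of 0.05:

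- rho 0.8: 0.90 × 0.95 = 0.855
- rho 0.9: 0.95 × 0.95 = 0.9025
- rho 0.95: 0.975 × 0.95 = 0.926

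**Step 5: power, as a generic illustration.** Assume a true effect of 0.5 SD of change, two-sided alpha 0.05 and 63 per group, which gives 80% power on the change score. None of these figures is from the plan.

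| Assumed rho | Baseline adjustment only | With R² = 0.05 added |
|---|---|---|
| 0.8 | 84.1% | 85.9% |
| 0.9 | 82.1% | 84.0% |
| 0.95 | 81.1% | 83.0% |

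**Step 6: direction.** With equal variances, the slope of change on baseline is rho - 1, which is negative: higher starting BMD goes with greater loss. That agrees in direction with the Background's statement about osteopenic patients.

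**The case against.** The strongest reply is that the plan names a contrast, not a model. Comparing changes is compatible with ANCOVA, because regressing change on treatment and baseline gives the same treatment estimate as regressing follow-up on treatment and baseline. This stands. A reader might infer that the investigators chose an unadjusted analysis, but the text does not say so. It is silent, and a plain change score is only its literal reading.

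Four other strong readings are tempting and also fail.

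- **The primary result would be biased or invalid.** A change-score comparison is unbiased under randomization. If the allocation factors matter, leaving them out makes it conservative.
- **Baseline imbalance enters the estimate in full.** That describes a follow-up-only analysis. Here only the fraction (1 - rho) remains.
- **ANCOVA can never lose precision.** Without treatment-by-covariate terms, the large-sample guarantee needs equal allocation or common slopes. No ratio is stated, and allocation also responds to completion rates in the groups, so equal allocation is not established.
- **The standard errors are certainly too wide.** That requires age, race or gender to predict hip BMD change within a turnover arm. The Background links race to turnover thresholds, but turnover already defines the arms, and the text does not show that these factors predict BMD change.

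It is also fair to say that the gain is small if hip BMD tracks closely over a year. None of this is an argument against adjusting. It limits the size of the claim. The study-design graph and procedures figure are attachments that were not available, so the point is confined to the text supplied.

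**Conclusion.** The point holds as a modest and nearly free improvement. No adjustment is specified for baseline total-hip QCT BMD or for the three patient-level allocation factors, although all are known before assignment.

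Against a literal change-score comparison, baseline adjustment would cut variance by about 2.5% to 10% for rho between 0.95 and 0.8, or 15% at rho 0.7. It would also remove the (1 - rho) carry-over of chance baseline imbalance. Adding age, race and gender helps only as far as they are prognostic, and the documents do not allow that share to be estimated. The figures rest on equal variances, equal allocation and an assumed rho. This is a matter of efficiency and prespecification, and it does not threaten the validity of the trial.

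**What to change.** State the model in the Primary Endpoint paragraph. Within each turnover arm, analyse 12-month total-hip QCT BMD by ANCOVA with treatment, baseline total-hip QCT BMD, age, race and gender. Change may be used as the outcome instead, since the treatment estimate is the same. Code race as it is coded for allocation. Completion rate is a property of the groups, not a patient baseline characteristic, so it does not enter as a patient covariate.

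Use 12 months for this comparison. Study Design says controls who complete a year without treatment will be offered treatment, so later control values need not come from untreated patients.

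For coronary calcification, use the same form with the baseline value as covariate, on one scale fixed in advance. Study Design lists the Agatston score, the square root of volume and density. The square root of volume is already planned and would serve.

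The cost is a few sentences of analysis wording, with no new scan, visit or data item.
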